TITLE: A Pilot Study on the safety and efficacy of Mifepristone for the prevention of relapses of alcohol drinking

PI: [name]

NCT02243709

IND121984

DATE: December 15 2014

CLINICAL PROTOCOL

A Pilot Study on the safety and efficacy of Mifepristone for the prevention of relapses of alcohol drinking

Principal Investigator:

[name], PhD

Brown University, Providence, RI

[contact]

[contact]

PROTOCOL SYNOPSIS

Objective: The primary objectives of the study include: A) Establish the safety and tolerability of using 600mg of mifepristone and 32.4mg yohimbine while consuming alcohol; and B) Demonstrate the feasibility of the study design and obtain an effect size to estimate a sample size for an appropriately powered larger R01 application using mifepristone and yohimbine together when administering alcohol.

Rationale: Glucocorticoids (GC) mediate adaptation to stress and regulate termination of the stress response through the hypothalamic–pituitary–adrenal (HPA) axis feedback action. The link between stress and chronic relapsing alcohol-use disorders (AUD) and substance-use disorders (SUD) has long been established in the addiction research field. Preclinical studies show the GC-receptor antagonist, mifepristone, reduces behavioral hyperexcitability during the acute phase of alcohol withdrawal, suggesting that mifepristone is a promising pharmacotherapy for alcoholic individuals to reduce the cognitive deficits caused by chronic alcohol use and withdrawal symptoms. In our preclinical studies, we showed that in conditions where stress is limited, mifepristone has no effect on alcohol intake, corroborating the hypothesis that GC blockade represents a key element in the preoccupation/anticipation (craving) stage of the addiction cycle. However, what remains unknown is the role of mifepristone in stress-induced craving and relapses of alcohol drinking in humans.

Overview of Study Design: The design will be a randomized within, crossover, double-blind, placebo-controlled human study with mifepristone in non-treatment-seeking-alcohol-dependent individuals. The study will be conducted in consecutive phases (Figure 1):

Visit#1: Screening;

Visit#2: Randomization and drug/placebo dispensed (for seven days);

Visit#3: First lab-session: single dose of yohimbine;

Visit#4: Washout period, follow-up (one month) and drug/placebo dispensed (for seven days);

Visit#5: Second lab-session, single dose of yohimbine; Motivational session (MET);

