Visit#6: Follow-up (one month); END of STUDY.

Study Population: Sixty-five non-treatment-seeking, alcohol-dependent participants will be recruited. Fifty-eight participants will be enrolled for screening with **50 participants (n = 50)** expected to complete the study. Participants will primarily be recruited via advertisements placed in local newspapers and posted on buses.

Safety Measurement/Parameters: Risks of medication side effects will be minimized through careful and detailed screening of participant. Signs of anxiety and stress, adverse events and vital signs will be assessed at each visit by psychometric assessments. Safety laboratory tests will be evaluated at baseline, and at the end of the study participants will receive a behavioral motivational session at the end of Visit 5.

Financial considerations: There will be no cost(s) to participate in this study. The study medications and all procedures that are not part of routine care, but are required for the study, will be provided to the participant. If eligible for the study, participants will receive \$25 for the randomization visit (Visit# 2) and for the follow-up visits (Visits #4 and #6). During the laboratory phase, at each visit (Visits #3 and #5) participants are compensated \$100 + another possible \$3/drink as incentive for not drinking (max \$24). Therefore, each participant may be compensated up to \$323 during the entire study period. Participants will be also compensated for their travel costs.

Specific Aims:

Aim 1: to assess the safety and tolerability of mifepristone and yohimbine while consuming alcohol.

Aim 2: to test the hypothesis that an increase in alcohol craving induced by yohimbine is antagonized by pre-administration with mifepristone.

Aim 3: to test the hypothesis that an initial priming drink and alcohol consumption induced by yohimbine is antagonized by pre-administration with mifepristone.

TABLE OF CONTENTS

PROTOCOL SYNOPSIS	2
TABLE OF CONTENTS	3
SPECIFIC AIMS	4
RATIONALE AND SIGNIFICANCE TO THE ALCOHOL FIELD	5
Stress and alcohol dependence	5
Clinical relevance	5
Pharmacological stress targets	5
Mifepristone	5
Stress-induced models	6
Integration: psychoneuroendocrinology and trauma factors	6
Significance for NIAAA	6
Innovation	6
The Investigator Team	7
The qualified medical personnel during the laboratory sessions	7
RESEARCH DESIGN AND METHODS	8
Overview of Proposed Research	8
Medications and Doses	8
Study Procedures	9
Data Analysis Plan	10

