Translating preclinical paradigms into effective models for assessing pharmacological approaches for stress-induced alcohol relapse in humans requires a comprehensive model capable of integrating: alcohol-proximal variables that influence drinking (withdrawal symptoms, craving), neuroendocrine variations (cortisol), and stress-risk factors (different temporal traumatic events). A comprehensive stress model is needed because emotional distress, neuroendocrine activation, stress-related genetic variations, craving, and alcohol consumption do not necessarily overlap in alcohol-dependent individuals. Mifepristone may be a valuable pharmacotherapeutic strategy for preventing relapse to AUD, and yohimbine is a pharmacological stressor capable of increasing craving, creating recall of traumatic memories, and altering neuroendocrine levels in alcohol-dependent individuals. As FDA-approved medications, both mifepristone and yohimbine have the advantage of being directly applicable to an alcohol clinical setting and being utilized in the translational efforts described in this application.

The overall objective of this study is to conduct a randomized pilot laboratory study consisting of a placebo-controlled assessment of the effects of 600 mg of mifepristone for a week, in a stress-induced condition triggered by a single dose of 32.4 mg of yohimbine in non-treatment-seeking-alcohol-dependent individuals. In the following specific aims, I propose:

Aim 1: to assess the safety and tolerability of mifepristone and yohimbine while consuming alcohol. Randomized participants will complete two alcohol laboratory sessions along with a battery of physiological and psychological assessments that measure adverse events and pharmacokinetic (PK)/pharmacodynamic (PD) interactions.

Aim 2: to test the hypothesis that an increase in alcohol craving induced by yohimbine is antagonized by pre-administration with mifepristone. To test this hypothesis, we will establish the effect of mifepristone on alcohol cue-elicited craving during a cue-reactivity (CR) experiment along with a series of physiological and psychological tests assessing alcohol craving.

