Medications and doses: Participants receive an oral dose of 600 mg of mifepristone or matching placebo for approximately seven days (plus three extra pills). Participants will receive detailed information on the study medications, including their current use and possible side effects. Mifepristone treatment in clinical setting has shown to be safe, tolerable, and acceptable⁸⁷⁻⁸⁹, including in participants suffering from depression, anxiety, and PTSD⁹⁰⁻⁹². On Days 7 and 44, all participants will receive a single oral dose of 32.4 mg yohimbine approximately one hour ($t_{max}=1$ hour) prior to the lab session. The oral dose of yohimbine for this study is based on prior studies in which yohimbine was administered to examine neuroendocrine probe in human studies^{57,93,94}. Ample data support the safe use of yohimbine to induce craving in alcohol-dependent individuals⁵⁷, and the safe induction of stress in PTSD veterans⁹⁵ and gamblers⁶⁰. We already obtained the Investigational New Drug (IND#121984) from FDA that determined that the clinical investigation of mifepristone and yohimbine while consuming alcohol is safe to proceed (see attaché letter form FDA). Our IND was also cross-referenced by the IND of Corcept Therapeutics (IND#059737) for chemistry, manufactory, pharmacological, and toxicology data of mifepristone (see attached letter form Corcept). Participants will receive detailed information on the study medications, including their current use and possible side effects.

STUDY PROCEDURES:

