Visits 3 and 5 (Stress-induction and Alcohol Laboratory Session): All procedures and responsibilities of each member of the research team are described in Appendix Z (page 3 and 5). Participants will be instructed not to consume alcohol for 24 hours and must have a BrAC of 0.00 prior to any assessment. A sample of salivary cortisol will be collected and a single oral dose of 32.4 mg yohimbine will be administered to participants. The lab-session will begin one hour later in order to allow yohimbine to take effect⁹⁶, at which time a second sample of cortisol will be collected. The CR will be run first, followed by the ASA (Assessments Schedule, Appendix Z). The PI will schedule Visit #3 and Visit #5 (alcohol laboratory sessions) only if [name] will be in proximity of CAAS laboratory. The PI will not schedule Visit #3 and Visit #5 if both study physicians are traveling or not in Providence.

Cue-reactivity (CR). The CR will be similar to previously published studies^{73,97-101}. The entire procedure takes about 45 minutes. The water trial provides a controlled baseline that controls for all aspects of stimuli and movement, except for the nature of the beverage. Next, participants will undergo two 3-minute alcohol cue exposure trials that will be identical to the water trial except that the glass of water will be replaced with their preferred alcoholic beverage and the bottle of water will be replaced with the appropriate commercially-labeled alcohol bottle. After every 3-minute beverage exposure, participants will rate their urge to drink alcohol by completing the alcohol urge and craving questionnaire (ACQ) to assess attention to the sight and smell of water and alcohol cues. Saliva (weight in cotton rolls, mg), heart rate (HR; beats/min) and blood pressure (systolic, diastolic, and mean arterial pressure-MAP) will be monitored continuously using a Dinamap Adult Vital Signs Monitor. After the conclusion of the CR, participants will undergo the ASA. Consistent with recommendations¹⁰², participants will be informed they will receive alcohol following the CR. The last of salivary cortisol (by spitting in a tube) will be collected at the end of the CR.

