Secondary outcomes: Craving measures included alcohol craving questionnaire short form-revised (ACQ-SF-R)². Values of the water trials for each dependent variable were inserted as covariate in the model (allowed for the dependent variable to be specific for alcohol), time coded: t_1 =alcohol trial 1 and t_2 =alcohol trial 2. In the bar laboratory, alcohol consumption was measured by number of drinks consumed (*t*-test). In the outpatient setting, alcohol consumption was measured by self-report using the timeline follow back method, reported as heavy drinking days and drinks per week.

All statistical analysis was performed after participants had their follow-up visit and the study database had been locked. All the statistical procedures were performed by IBM SPSS Statistics for Windows, version 27 with Macro MEMORE extension⁹ (IBM Corp., Armonk, NY, USA) and GraphPad Prism (v.5) was used to generate figures (La Jolla, CA, USA). The effect sizes were calculated as η^2 for GLM and Cohen *d* for *t*-test. All statistical tests were two-tailed, and statistical significance was accepted if an alpha value $p<.05$ was obtained.

For all outcomes, we utilized an intention-to-treat (ITT) approach, where participants were examined based on their *a priori* randomized protocol and received at least one dose of the study medication

(mifepristone or placebo)³. All analyses were conducted using Generalized Estimating Equations (GEE)⁴ with robust standard errors, and an unstructured correlation matrix, unless noted.

Power

This was a proof-of-concept trial to demonstrate the feasibility of the combined study design, the safety and tolerability of mifepristone and yohimbine while consuming alcohol, and the potential value of testing mifepristone in an appropriately-powered larger RCT. In selecting a target sample size, we balanced power considerations and feasibility given the translational nature of this trial. Because of the within-subjects design, power to test the effects of study drug is optimized for this modest sample size (originally $N=20$ then, after additional funding, increased to $N=32$). For the safety and tolerability outcomes (primary) adverse events difference was detected based on a judgement concerning the minimal effect which has clinical relevance in the management of patients. In a noninferiority trial, the exact sample size cannot be fixed in advance because it depends upon the chosen stopping guideline⁵.

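### Adjusting alcohol-trial craving for a water-trial score taken after both drugs gives the stated cue-specific effect only if mifepristone leaves water-trial craving unchanged or the water slope is 1

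*SAP*

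**What the plan says.** **Order of events.** Study drug is handed out at Visit 2: "Randomization and drug/placebo dispensed (for seven days". On both session days "all participants will receive a single oral dose of 32.4 mg yohimbine approximately one hour" before the session (Protocol, Medications and doses). The procedures for Visits 3 and 5 confirm the order: "The lab-session will begin one hour later in order to allow yohimbine to take effect". The water trial follows, then two alcohol trials, with the ACQ completed after each exposure.

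**Role of the water trial.** Protocol, Cue-reactivity: "The water trial provides a controlled baseline that controls for all aspects of stimuli and movement, except for the nature of the beverage".

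**Analysis.** SAP, Secondary outcomes: "Values of the water trials for each dependent variable were inserted as covariate in the model". The same sentence gives the reason, which is to make the dependent variable specific to alcohol. By default, SAP analyses use GEE with robust standard errors and an unstructured correlation matrix, unless noted otherwise.

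**Aim and use of the result.** Aim 2 is "to test the hypothesis that an increase in alcohol craving induced by yohimbine is antagonized by pre-administration with mifepristone". To test it, "we will establish the effect of mifepristone on alcohol cue-elicited craving during a cue-reactivity (CR) experiment". Objective B in the Protocol Synopsis is partly to "obtain an effect size to estimate a sample size for an appropriately powered larger R01 application". The protocol's Data analysis section names craving, measured by the ACQ, as one of the two outcomes for which an effect size is sought.

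**The concern.** A covariate measured before treatment sharpens a treatment comparison without changing what is compared. The water-trial score is not of that kind. The protocol treats it as a baseline, but both drugs have been taken by then, and Aim 2 supposes that mifepristone acts on craving raised by a drug given an hour earlier. An effect on water-trial craving is therefore possible. The SAP neither assumes that it is absent nor plans to estimate it.

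If mifepristone lowers craving in general, adjustment for water removes only part of that general effect. The remainder would be read as cue-specific. A reader of the adjusted result alone could not tell a true cue-specific effect from the residue of a general one, and that number could be carried into the sizing of the next trial.

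**Working it through.** **The plan's own figure.** The SAP's N=32 (originally 20) comes with no craving effect, SD, correlation or power, so it cannot be reproduced. For scale only, a paired t-test at N=32, two-sided 5%, has 80% power for a standardised difference of about 0.51.

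**Algebra.** Let dA and dW be the mifepristone-minus-placebo effects on alcohol-trial and water-trial craving, and b the fitted water slope.

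- Adjusted coefficient = dA − b·dW
- Cue-specific effect (alcohol minus water) = dA − dW
- Difference = (1 − b)·dW

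The difference is zero only if dW = 0 or b = 1.

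**Assumed inputs.** The documents give neither dW nor any correlation. I took dA = 0.5 SD, total variance 1, two sessions, and one water and two alcohol trials per session. The within-session water-alcohol correlation is the sum of person and session variance, split as follows:

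- 0.4: 0.3/0.1, 0.1/0.3 (and 0.2/0.2 for the estimates)
- 0.6: 0.5/0.1, 0.4/0.2, 0.3/0.3
- 0.8: 0.7/0.1, 0.6/0.2, 0.5/0.3, 0.3/0.5
- 0.9: 0.8/0.1, 0.7/0.2, 0.5/0.4

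The model was a GEE on the four alcohol trials with unstructured correlation and terms for treatment, period, time and water ACQ. Rejection rates use N=32 and Mancl-DeRouen standard errors with a t reference.

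| Correlation | Fitted b | Adjusted estimate, wholly shared (truth 0) | Adjusted estimate, half shared (truth 0.25) | Rejection, wholly shared |
|---|---|---|---|---|
| 0.4 | 0.36–0.40 | 0.30–0.32 | 0.40–0.41 | 34%–45% |
| 0.6 | 0.55–0.59 | 0.21–0.23 | 0.35–0.37 | 26%–32% |
| 0.8 | 0.78–0.80 | 0.10–0.11 | 0.30–0.31 | 12%–15% |
| 0.9 | 0.89–0.90 | 0.05 | 0.28 | 8%–9% |

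Here truth means the alcohol-minus-water effect. Check on the first row: 0.5 − 0.40 × 0.5 = 0.30 and 0.5 − 0.36 × 0.5 = 0.32. In the wholly shared case the direct alcohol-minus-water contrast rejects in 4%–6%. When the effect is purely cue-specific (dW = 0), the adjusted estimate is 0.50.

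The slope also mixes between-person and within-person association. With dA = 0.5 and dW = 0.3 fixed, raising only the between-person correlation from 0.6 to 0.9 moved b from 0.62 to 0.79 and the adjusted effect from 0.32 to 0.27.

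**What it does to sizing.** In a paired design at 80% power, n = ((1.96 + 0.84) × SD / effect)². Take the SD of the within-person difference as 1, dA = 0.5, dW = 0.3 and b = r = 0.6:

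- alcohol-trial effect: 0.50, SD 1, n = 32
- adjusted: 0.5 − 0.6 × 0.3 = 0.32, SD √(1 − 0.36) = 0.80, n = 50
- alcohol minus water: 0.20, SD √(2 − 1.2) = 0.894, n = 157

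With dW = 0 the effect is 0.50 each time, and n is 32, 21 and 26.

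**Separate check: type I error of the craving GEE.** There were 6,000 replicates, with normal or skewed errors. Plain robust standard errors with 1.96 gave 8.2%–9.0% at N=32 (6.8%–7.3% at 50). Mancl-DeRouen with a t reference gave 5.0%–5.9% (4.8%–5.4% at 50).

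**The case against.** The best defence is that the documents do name their target. The SAP's rationale for the covariate, the cue-elicited wording in Aim 2 and the water trial's role as a control all point to cue-specific craving. That stands. A reader might infer that the SAP leaves the craving target undefined, and the documents do not support that reading. The narrower point survives: naming the target does not make covariate adjustment deliver it.

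A reader might also take a low rejection rate for a wholly shared effect as lost power. That holds only if total craving is the target. For the stated target the true effect is then zero, few rejections are what one wants, and the error is that there are too many.

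Nor is it an inconsistency that the SAP's time coding covers only the two alcohol trials. The ACQ ratings around the priming drink belong to the self-administration paradigm.

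The defence is also right that every size above is assumed and that nothing is lost if dW = 0. The simulations use 32 complete participants, while the SAP does not say whether 32 are enrolled or complete, and dropout is not modelled. Objective B does not itself name craving; the link comes from the Data analysis section. Finally, the GEE point is conditional: the SAP's default has an exception clause, it also mentions GLM effect sizes, and the protocol plans ANCOVA.

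**Conclusion.** The concern holds in limited form. The water-trial score follows treatment, so the adjusted coefficient is the stated cue-specific effect only if dW = 0 or b = 1. The documents do not give dW, so they do not show that the analysis is biased, only that it could be and that the plan would not reveal it. If the effect were wholly shared, the adjusted model at N=32 would wrongly indicate a cue-specific effect in roughly 35% to 45% of trials at correlation 0.4, falling to 8% to 9% at 0.9. If it were purely cue-specific, there is no loss.

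The standard-error point is independent of the water covariate and applies only if craving is analysed by the default GEE. It was not examined for other outcomes; the SAP assigns adverse events a chi-square test and laboratory drinks a t-test.

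Weight is low. Craving is a secondary outcome, and the primary safety results are untouched.

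**What to change.** 1. Keep the water-adjusted model.
2. Add one model with the water trial and both alcohol trials as outcomes, with treatment-by-trial terms and a period term. Report three estimates: the mifepristone effect on water-trial craving, the effect at the alcohol trials, and the direct alcohol-minus-water contrast. With complete data, each is a period-adjusted per-person contrast with t on N − 2 degrees of freedom; in simulation at N=32 such contrasts had type I error of 4.5%–5.3%.
3. Label these as supplementary, since the SAP is written in the past tense and refers to a locked database. State which estimate is offered for sizing the next trial.
4. State that none of them isolates the yohimbine-induced part of craving, because everyone receives yohimbine at both sessions.
5. If craving uses the default GEE, apply a small-sample correction such as Mancl-DeRouen with a t reference, or use a mixed model with Kenward-Roger degrees of freedom.

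**Cost.** One extra model on ACQ data already collected, some wording, and slightly wider craving intervals. The direct contrast has less power than the adjusted model when the correlation is low. For a purely cue-specific 0.5 SD effect it is 52%–54% against 76%–83% at 0.4, and 94%–95% against 96%–98% at 0.8. That is the reason to keep the adjusted model.

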Center Alcohol and Addiction Studies

Brown University

TITLE: A Pilot Study on the safety and efficacy of Mifepristone for the prevention of relapses of alcohol drinking

PI: [name]

NCT02243709

IND121984

DATE: December 15 2014

Statistical analysis

Distributional characteristics of outcome measures were examined to evaluate similarity to the normal distribution, detailed descriptive analysis of demographics, substance use, and clinical characteristics were conducted. Comparisons with these characteristics, in relation to enrolled versus completer status, were performed using *t*-tests to analyze continuous variables (e.g., age) and Chi square (χ^2) for categorical variables (e.g., sex, race, smoking status). Attrition rates between the screening visit and follow-up visit were examined descriptively to assess for potential bias. In addition, a logistic regression was performed to test for possible bias due to period (A/B: placebo first, then mifepristone and B/A: mifepristone first, then placebo) or medication carryover (1: placebo and 2: mifepristone), as done in our prior cross-over trial¹.

Primary outcomes: safety and tolerability of oral administration of mifepristone was assessed after 7 days in outpatient setting, and when it was administered with yohimbine and alcohol during the laboratory paradigms. These analyses included comparing the number of adverse events (AEs) between the mifepristone and placebo condition via a χ^2 test. The results were presented using summary statistics such as number of subjects (*n*); mean (*M*); standard deviation (*SEM*) or frequency distributions (%).

Primary outcomes: safety and tolerability assessed by the number of adverse events (AEs) of oral administration of mifepristone was assessed after 7 days in an outpatient setting, and when it was administered with yohimbine and alcohol during the laboratory paradigms. Additional safety and tolerability analysis included hemodynamic response, alcohol pharmacokinetics, and subjective effects of alcohol between the mifepristone and placebo condition (χ^2 test).

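### The SAP applies ITT to the primary adverse-event comparison with exposure tested per person, so a mifepristone-assigned period with no mifepristone taken may be analysed as mifepristone

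*SAP*

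**What the plan says.** The analysis-set rule is in the SAP's Statistical analysis section, in the paragraph just before Power. It opens "For all outcomes, we utilized an intention-to-treat (ITT) approach, where participants were examined based on their" and makes no exception for safety. The condition for inclusion is that a participant "received at least one dose of the study medication", and the bracket that follows lets either mifepristone or placebo qualify. GEE is then named as the default method unless otherwise noted.

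The primary outcome, earlier in the same section, is safety and tolerability, analysed by "comparing the number of adverse events (AEs) between the mifepristone and placebo condition via a" chi-square test. The design has two sequences ("A/B: placebo first, then mifepristone and B/A: mifepristone first, then placebo"), so each completing participant contributes one period per condition.

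Neither the SAP nor the protocol's Data analysis section defines a safety set by condition, an AE analysis by treatment taken, a denominator for the AE comparison, or a rule for periods never started. The protocol's Compliance paragraph describes adherence counselling and blister packs, but neither document uses exposure in an analysis.

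**The concern.** In a parallel-group trial, requiring one dose of study medication shows that a participant was exposed to the assigned arm. The reference the SAP gives for its ITT approach is a parallel-group reporting guideline. In a crossover the same requirement, applied once per person, says nothing about exposure in each period. Someone who took placebo capsules in one period and none of the mifepristone capsules in the other still qualifies, and analysis as randomised places that second period under mifepristone.

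For craving and drinking, ITT answers a sensible question. For tolerability, counting unexposed periods as mifepristone moves the AE difference towards zero, which favours a conclusion of safety. The SAP's Power section also uses non-inferiority language without stating a margin. In that setting, dilution towards no difference is anti-conservative. Capsules are dispensed for about a week between visits, and the protocol's Compliance paragraph itself plans a discussion of missed doses, so such periods are possible.

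**Working it through.** **The plan's own figures.** There is none to reproduce on this point. The SAP's sample size of 32 comes with no AE rate, margin, effect size or target power, so no planned AE difference can be recovered from it.

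**Which method governs AEs.** GEE is the default only where nothing else is noted, and for AEs a chi-square test is noted. GEE on observed periods therefore cannot be assumed to settle the denominator. It would also not remove a period that was attended and observed but in which no capsule was taken.

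**Inputs, all assumed for illustration.** True AE risk 40% on mifepristone and 20% on placebo, so a true excess of 20 points. f is the share of periods affected, set at 7% and 25%. With 32 periods per condition these are about 2 periods (0.07 × 32 = 2.2) and 8 periods (0.25 × 32 = 8). The protocol's planned fall from 58 to 50 participants cannot supply f. It is counted from screening, before randomisation at Visit 2, and loss is not the same as an unexposed period that is still counted.

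**Case A: period observed, no mifepristone taken, analysed as mifepristone.** Yohimbine and alcohol are given in both laboratory sessions, so the placebo risk is a more natural assumption for these periods than zero.

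Observed risk = (1 − f) × 0.40 + f × 0.20

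Observed excess = (1 − f) × 0.20

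- f = 7%: 0.372 + 0.014 = 38.6%; excess 0.93 × 20 = 18.6 points.
- f = 25%: 0.300 + 0.050 = 35%; excess 0.75 × 20 = 15 points.

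**Case B: mifepristone period never started, kept in the denominator and scored as no AE.**

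Observed risk = (1 − f) × 0.40

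- f = 7%: 37.2%; excess 17.2 points.
- f = 25%: 30%; excess 10 points.

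**Case C: period never started, left out of the denominator.** If the loss is unrelated to AE risk, the excess stays at 20 points for any f.

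**Case D: placebo period never started (loss after mifepristone first), scored as no AE.**

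Observed placebo risk = (1 − f) × 0.20

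- f = 7%: 18.6%; excess 40 − 18.6 = 21.4 points.
- f = 25%: 15%; excess 40 − 15 = 25 points.

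| Handling | Excess, f = 7% | Excess, f = 25% |
|---|---|---|
| A. Unexposed, counted as mifepristone | 18.6 | 15 |
| B. Missing mifepristone period scored as no AE | 17.2 | 10 |
| C. Missing period left out | 20 | 20 |
| D. Missing placebo period scored as no AE | 21.4 | 25 |

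The SAP's wording does not choose among these cases.

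**The case against.** The strongest reply is that the SAP never says a participant who did not start the mifepristone period is counted under mifepristone. The AE comparison is by condition, and the primary outcome is tied to mifepristone as administered. The one-dose condition could also be meant per condition. If never-started periods are simply absent from the table, they dilute nothing. This stands against the stronger inference a reader might draw, that the AE result is biased and always in the direction that flatters safety. The documents do not establish that, and case D shows that the direction can reverse. The reply does not remove the point: the literal rule is per person, and it also covers periods that were observed but unexposed.

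A second reply is that low exposure is not in itself a reason to exclude. The protocol's Protection of Human Subjects section provides for withdrawal when AEs are serious or intolerable, so a short mifepristone period may itself be an AE case. Removing such periods would hide harm. This stands in full. Any safety set must keep everyone with at least one dose in the period, so dilution from partial adherence will remain.

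Third, the protocol supports adherence with counselling and blister packs, and f may be small. That is fair; the documents give no rate either way.

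**Conclusion.** The concern holds as a defect in the analysis-set rule. ITT covers the primary AE comparison, and the exposure test does not identify exposure to each condition in a two-period crossover. As written, it permits a mifepristone-assigned period without mifepristone to be analysed as mifepristone. Where that happens and such periods carry the placebo risk, the excess shrinks by the factor (1 − f): from 20 points to 18.6 at f = 7%, or to 15 at f = 25%, under assumed risks of 40% and 20%.

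The actual size is unknown, because the documents give no adherence rate, placebo AE risk or loss by period. They do not show that dilution occurred, or that the handling of missing periods would work in one direction only. Because this is the primary outcome and the change is small, the rule should be corrected.

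**What to change.** Keep ITT for craving and drinking. For AEs, make a per-condition safety set the primary analysis:

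- A participant counts in a condition only if at least one dose of that condition's capsules was taken in that period.
- AEs are attributed to the agent actually taken.
- Never-started periods are left out of that condition's denominator, not scored as zero AEs.
- Everyone with at least one dose in the period stays in, including those who stopped early because of AEs.

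State the resulting denominator for each condition. Report the ITT version as a sensitivity analysis, and describe exposure by period where capsule records exist. The protocol describes dispensing blister packs but not their return or a capsule count, so those records should be confirmed first. Exposure summaries should stay descriptive, because stopping can be caused by an AE.

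The cost is SAP wording and, if results are already tabulated, a re-tabulation, plus slightly fewer person-periods in the safety table.
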